7.5 STORAGE AND ANALYSIS OF SAMPLES

Research blood samples will be taken as part of the trial to evaluate the biological mechanisms in patients with moderate to severe ARDS.

^b On Day 3 (+2d)

Samples will be taken in both dexamethasone arm, and usual care arm of the trial, at two time points. The first sampling time point is referred to as baseline (defined as soon as possible, after consent, and randomisation, before dexamethasone administration in the intervention arm. The second sampling time point is referred to as Day-3(+2) post randomisation.

Baseline:

- One RNA tube (2.5ml)
- One Serum tube (white or brown top tube, 4ml)
- One plasma EDTA or Citrate tube (red, 2ml)

And

Day-3 (+2) post randomisation:

- One RNA tube (2.5ml)
- One Serum (white or brown top tube, 4ml)
- One plasma EDTA or Citrate tube (red, 2ml)

Further details on the sample handling, storage and analysis can be found in the GuARDS specific Biological Sample Laboratory Work Instruction. RNA and Serum samples will be sent to laboratories in IRR, University of Edinburgh and plasma samples will be sent to Institute for Experimental Medicine, Queen's University of Belfast.

RNA samples will undergo transcriptomics to understand changes in gene expression in ARDS patients. Several methods will be used to explore differences in inflammation and immune function in ARDS patient groups in the plasma and serum samples.

If a sample is not taken, reasons will be collected in the eCRF but it will not be treated as a protocol deviation.

8. DATA COLLECTION

We will use a bespoke web-based electronic case report form, with a full data dictionary, automatic and manual data queries and a full audit trail, to ensure data captured are consistent, reliable and fully compliant with all Good Clinical Practice and any other regulatory requirements. We will seek consent from patients for longer-term follow-up up to 6 months using routine databases. We have previously used this approach in critical care trials, successfully. Long-term mortality, and Health service use since hospital discharge will be collected using NHS Digital data linkage for sites in England, edRIS linkage for Scotland, SITES for Northern Ireland and SAIL Databank for Wales. For all linkages, the guidance proposed by each of the organisations will be followed.

Data will be collected by a qualified and delegated healthcare practitioner within the hospital setting or via telephone call.

8.1 Baseline data

Data including initials;; date of birth; sex at birth; height (to calculate ideal body weight);; GP Address; Postcode to determine regional index of multiple deprivation, self-reported ethnicity, hospital site; pre-existing co-morbidity; ARDS risk factor⁴, APACHE II score; Sequential Organ failure Score³³; ventilator settings at randomisation, measure of ARDS, Use of adjunctive therapies,.

Baseline data thus includes key intersectional data considered within the NIHR-INCLUDE roadmap³⁴. This will enable us to monitor inclusion of under-served groups in the trial.

8.2 Daily data during ICU stay

Mechanical ventilation status, information about organ support as defined by the UK Critical Care Minimum Data Set; drug-related adverse events (upper GI bleed and days of antibiotic therapy); ICU length of stay; secondary outcome variables.

8.3 Hospital and follow-up

Data will be collected on hospital length of stay; survival; long-term follow-up outcome measures including health care usage (completed at 60, 90 and 180days), and HRQoL questionnaires (completed at 60, 90 and 180 days). Questionnaires may be carried out in person (e.g., on the ward if the patient is an inpatient in the participating hospital at the time of follow up) or via telephone by a qualified person in the research team. Data will be recorded in an eCRF. HRQoL Questionnaires may be sent via email for patients to complete in their own time with answers directly populated to the eCRF.

Long-term mortality and health care use since hospital discharge will be collected using NHS Digital data linkage for sites in England, edRIS linkage for Scotland, SITES for Northern Ireland and SAIL Databank for Wales Databank for Wales. For all linkages, the guidance proposed by each of the organisations will be followed.

Trial patients will be informed of study questionnaire via telephone and asked their preference on how to complete the questions. Where a patient is unable to complete a questionnaire, their Personal legal representative may complete on their behalf or data will be recorded as missing and not treated as protocol deviation. Sites may attempt to follow up with patients three times before they are considered lost to follow-up.

8.4 SOURCE DATA DOCUMENTATION

Source data is defined as all information in original records and certified copies of original records or clinical findings, observations, or other activities in a clinical trial necessary for the reconstruction and evaluation of the trial. Source data are contained in source documents. Source documents are original documents, data and records where source data are recorded for the first time. The source data will be the patient's medical records, electronic records, data collection sheets and completed questionnaires. A record of where the source data can be found will be detailed in a separate source data plan.

8.5 CASE REPORT FORMS

Study data will be recorded on the electronic CRF by members of the research team at each site. Follow-up study data collected centrally will also be recorded on the eCRF. Paper data collection sheets may be used if required by sites.

Case report forms must be reviewed and approved by the ACCORD Monitor prior to use (see ACCORD SOP CR013 CRF Design and Implementation).

NOTE: All electronic case report forms are subject to Co-Sponsor approval (see section 8.3).

8.6 TRIAL DATABASE

A trial database/ECRF developed by the Clinical Trials Unit in Edinburgh will be used to collect all study data. This will be built in accordance with ECTU SOPs. This will be hosted by the University's Enterprise Server Visualisation and Hosting Service which is physically located at the University of Edinburgh Data Centre on the King's Buildings Campus. Individuals will be issued log-in details and access will be restricted to necessary fields only. The study teams at site involved in follow-up data collection or data entry will enter data. Participants contact details will be encrypted for storage in the database. Following data analyses, the database will be archived by appropriately trained software developers at

ECTU. This archived database will be stored on University of Edinburgh servers once user access has been disabled. Access to the archived database will be controlled by the Chief Investigator.

9. DATA MANAGEMENT

9.1 Data Management Plan

All aspects of data collection, data processing (entry/uploading, cleaning, and query management), and the production of the final dataset ready for analysis and/or archiving will be detailed in a separate Data Management Plan (DMP).

9.2 Personal Data

The following personal data will be collected as part of the research:

Study ID, date of birth, sex at birth, Postcode (to determine index of multiple deprivation), self-reported ethnicity, email address, telephone number, death record, and unique hospital number (CHI/NHS). Personal data detailed will be stored on an Edinburgh Clinical Trials Unit (ECTU) secure database which is compliant with Sponsor SOPs. Only named research staff will have access. Data will be stored for a period of 5 years after the trial has finished follow-up.

Personal data required for follow up trial procedures (Study ID, date of birth, sex at birth, Postcode (to determine index of multiple deprivation), death record, telephone number and, unique hospital number (CHI/NHS) and the name of the Personal Legal Representative who gave their consent) will be stored securely by the research team at each recruiting site for up to 5 years after the trial has finished follow-up.

9.3 Data Information Flow

A bespoke web based electronic data capture system will be used, hosted by ECTU. Site staff will be given training on data entry requirements as part of site set up, and only given access to the live database after they have accessed the training database and completed the training. Written instructions for data entry will also be filed in the ISF to be used by site staff for reference.

The data manager will review the data entered, raise any data queries identified from the data management plan with the study sites and will liaise with the trial statistician to ensure all queries are raised and resolved prior to database lock. The trial manager will document database lock prior to the final dataset being sent for analysis. A separate Data Management Plan will be prepared for the trial detailing the checks to be undertaken.

9.4 Data Storage

The research team will store personal data as follows:

- i) All paper files containing personal data will be held in site files. These files will be held securely at each research site. Access to the research documents will be by the research team only.
- *ii*) Electronically on an Edinburgh Clinical Trials Unit secure database compliant with Sponsor SOPs. Named researchers will have access.

Personal data will be stored for five years to allow for inspection and audit of data if required. Data will be uploaded by a suitably qualified person at ECTU following approved standard operating procedures. This will be cross checked prior to locking of the database for analysis.

9.5 Data Retention

All study documentation will be kept for a minimum of 5 years from the protocol defined end of study point. When the minimum retention period has elapsed, study documentation will not be destroyed without permission from the sponsor.

9.6 Disposal of Data

Study data will be archived by a senior software developer at ECTU following sponsor approved SOPs. This will be fully documented in the Data Management Plan.

9.7 External Transfer of Data

Data collected or generated by the study from consenting individuals may be transferred to external individuals or organisations outside of the Sponsoring organisation(s). It may be provided to researchers running other research studies out with NHS Lothian/University of Edinburgh. Organisations and researchers will only use anonymised participant information to conduct research in accordance with the UK Policy Framework for Health and Social Care Research. Where this information includes identifiable information, it will be held securely with strict arrangements about who can access the information.

We intend to perform data linkage with nationally held databases to find out about the participant's long term health. In order to identify them on these databases we will use their NHS/CHI number and other personal details.

9.8 Data Controller

The University of Edinburgh and NHS Lothian are joint data controllers along with any other entities involved in delivering the study that may be a data controller in accordance with applicable laws (e.g. the site).

9.9 Data Breaches

Any data breaches will be reported to the University of Edinburgh ([contact]) and NHS Lothian ([contact]) Data Protection Officers who will onward report to the relevant authority according to the appropriate timelines if required.

10. STATISTICS AND DATA ANALYSIS 10.1 SAMPLE SIZE CALCULATION

10.1.1 Primary outcome event rates

We conducted a systematic review of ARDS RCTs commencing recruitment after the 1994 American European Consensus Conference ARDS definition. We identified 150 ARDS RCTs, and 28 of these RCTs used mortality as primary outcome for sample size calculations. Based on this systematic review, we expect 40% control arm mortality at 60 days¹¹.

10.1.2 Estimated treatment effects

To date there have been 9 RCTs (8 non-COVID ARDS RCTs^{13,15,35-41}, including one septic shock trial reporting glucocorticoid effects in the ARDS sub-populations). With fixed effect meta-analysis, the overall risk ratio (95% CI) was 0.75 (0.59, 0.94), favouring glucocorticoid treatment in ARDS (Figure 1). In the corresponding random effect meta-analysis, the overall risk ratio (95% CI) was 0.83 (0.70, 0.99), again favouring glucocorticoid treatment in ARDS. In the DEXA-ARDS Trial that enrolled a similar target population using the same dexamethasone dose, the absolute risk reduction (ARR) in hospital mortality was 15.3%¹³.

For our sample size estimations, we have used a conservative estimate of 8% ARR for expected treatment effect. Our primary rationale being that in our systematic review of 150 ARDS RCTs¹¹, no ARDS RCT of pharmacological interventions to-date have reported an observed ARR of 10% or higher⁴².

10.1.3 Sample size estimation

With a frequentist group-sequential design, we have planned and adjusted our sample size for four analyses of primary outcome (at 50%, 65%, 80% and 100% sample size), including three interim analyses. The design uses a Hwang-Shih-DeCani spending function, of which the lower bounds are non-binding (routine 'gsDesign' in R version 4.0.5 (2021-03-31 for Mac). Based on these considerations, to achieve a power of 90%, for the primary outcome of mortality at 60 days (binary yes/no outcome) and a (teosided type 1 error rate of 0.05 without continuity correction⁴³, we would require 1656 patients. Further, based on previous UK ICU RCTs, we expect less than 3% loss to follow-up at 60 days. Therefore, we propose a maximum sample size of 1708 patients (around 854 patients/arm). The first interim analysis is expected to occur when 828 have complete 60-day outcomes, the 2nd interim analysis at 1077, the 3rd at 1325 and the final at 1656 (which is 1708 assuming 3% missing vital status). This is assuming the control rate is 40%. The z-values for stopping for futility are 0.47, 0.87, 1.35 and (for the final analysis, if reached 2.02); and for stopping for efficacy 2.75, 2.62, 2.39 and 2.02 (for the scheduled interim analyses at 50%, 65%, 80%, and 100% of information achieved).

10.2 PROPOSED ANALYSES

As highlighted in Section-3 GuARDS Trial is a parallel group, allocation concealed, open label, pragmatic, group sequential design randomised controlled trial⁴⁴, with internal pilot, with frequentist analyses.

One experimental treatment (intravenous dexamethasone) is compared with usual care (control) arm. Prior to the first formal interim analysis, we will generate a detailed Statistical Analysis Plan (SAP), which will include details of how missing data will be accounted for in the analyses.

Analyses will be two-sided and tested at an a priori significance level of p=0.05. The primary analyses will be conducted on an intention-to-treat basis, with all randomised patients being analysed in the group to which they were allocated, regardless of the subsequent treatment they received. Results will be reported in accordance with Consolidated Standards of Reporting Trials guidance for parallel group clinical trials⁴⁶.

We will describe baseline characteristics, follow-up measurements and safety data, using suitable measures of central tendencies; means and medians with the associated standard deviations and interquartile ranges for continuous data; and frequencies and proportions for categorical data (including binary data).

The primary outcome for the randomised groups will be analysed using a logistic regression model, adjusted for age, and severity of hypoxaemia at baseline as two pre-defined baseline prognostic covariates. Analysis of secondary outcomes will involve fitting models appropriate to the type of outcome measure (i.e. time-to-event, binary, continuous).

Subgroup analyses will be provided on the primary outcome, for baseline patients features age category (≤65 years vs. >65 years), sex, comorbidities (number, and diabetes status), shock status, pneumonia diagnosis, baseline illness severity, and ARDS features (pulmonary

vs extra pulmonary, sepsis status, baseline mechanical ventilation status, severity of hypoxaemia, and extent of chest radiology involvement). These analyses will be based on an intention-to-treat population and will be restricted to participants with non-missing subgroup data at baseline.

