5.5 RANDOMISATION

5.5.1 Randomisation Procedures

Randomisation will be performed by a member of the research team at each site using an automated web-based system developed by the ECTU, using variable block sizes and stratified by centre, ensuring allocation concealment. Participants will be randomised at 1:1 allocation ratio to either Usual Care alone or Dexamethasone plus Usual Care intervention. This is an open-label trial where patients, clinicians and assessors are aware of the treatment assignment post randomisation.

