7.2 STUDY ASSESSMENTS

See Table 3 for a summary of all study specific assessments.

Baseline data will be recorded (Age, sex, height, index of multiple deprivation, self-reported ethnicity, smoking status in the past 6 months, hospital site, pre-existing co-morbidity; ARDS risk factor, APACHE II score; Sequential Organ failure Score; mode of ventilation and ventilator settings, measure of ARDS, use of adjunctive therapies. Baseline data thus includes key intersectional data considered within the NIHR-INCLUDE roadmap. This will enable us to monitor inclusion of under-served groups in the trial.

Daily data during ICU stay to report secondary outcomes will be recorded for all patients (mechanical ventilation status; respiratory, renal, cardiovascular organ support as defined by the UK Critical Care Minimum Data Set; length of stay (ICU (includes HDU), and hospital); non-trial glucocorticoid treatment; safety outcomes (upper GI bleed and number of days of antibiotic therapy); and adverse events as per the adverse event reporting guidance.

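### The primary model leaves out centre, the only stratification factor, and a severity score already collected; stated power stands, but some extra power is given up without a stated reason

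*Protocol*

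**What the plan says.** Protocol section 5.5.1 describes web-based allocation "using variable block sizes and stratified by centre", and no other stratification factor is named. Section 3.2 expects at least 60 sites.

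Section 10.2 gives the primary analysis as a logistic regression for 60-day mortality, "adjusted for age, and severity of hypoxaemia at baseline as two pre-defined baseline prognostic covariates". Centre does not appear. Sections 7.2 and 8.1 list the baseline data, which include "APACHE II score; Sequential Organ failure Score". In section 10.2, baseline illness severity returns only as a subgroup factor.

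The protocol does not say why centre or illness severity is outside the primary model. It promises a statistical analysis plan before the first interim analysis and names missing data as a topic for it. The prognostic covariates, however, are already fixed here by number and name.

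**The concern.** When allocation is balanced within centres and centres differ in mortality, part of the outcome variation is balanced between the arms by design. A model without centre does not credit that balance, so its standard error for the treatment effect is somewhat too large and the test somewhat conservative. The four looks compare Z with fixed boundaries that assume unit variance. If dexamethasone works, an understated Z makes crossing for efficacy less likely and crossing for futility more likely.

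The severity score raises a different matter. Adding a strong predictor to a logistic model does not narrow the standard error of the log odds ratio. It moves the conditional log odds ratio further from zero by more than the standard error grows, so the gain appears in Z and in power. Since the scores are collected anyway, leaving both out gives up power that would need no new data.

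**Working it through.** **1. Reproduce the plan's own figure.** Inputs from the protocol: control mortality 40% (section 10.1.1: "we expect 40% control arm mortality at 60 days"); effect 8 points, so 32% on dexamethasone (10.1.2: "we have used a conservative estimate of 8% ARR for expected treatment effect"); power 90% (10.1.3: "to achieve a power of 90%, for the primary outcome of mortality at 60 days (binary yes/no outcome"); two-sided 5% (10.2: "Analyses will be two-sided and tested at an a priori significance level of p=0.05"); 1:1 allocation (5.5.1); looks at 50, 65, 80 and 100%.

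Fixed design, no continuity correction, mean proportion 0.36:

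n per arm = [1.96 × √(2 × 0.36 × 0.64) + 1.2816 × √(0.40 × 0.60 + 0.32 × 0.68)]² / 0.08² = 754.5, so 755 per arm and 1510 in total.

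The protocol does not state the parameters of its Hwang-Shih-DeCani spending function. Values of -4 for efficacy and -2 for non-binding futility reproduce the stated boundaries:

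| Look | Efficacy, stated / computed | Futility, stated / computed |
|---|---|---|
| 50% | 2.75 / 2.750 | 0.47 / 0.471 |
| 65% | 2.62 / 2.618 | 0.87 / 0.871 |
| 80% | 2.39 / 2.386 | 1.35 / 1.347 |
| 100% | 2.02 / 2.025 | 2.02 / 2.025 |

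The inflation factor is 1.096, giving a total of 1655 against the stated 1656. Then 1656 / 0.97 = 1707.2, or 1708 in two equal arms.

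At 1656 patients the expected final Z is 0.08 / √(2 × 0.36 × 0.64 / 828) = 3.39, and power with the stated boundaries is 90.0%. No covariate enters this calculation, so leaving covariates out cannot lower it.

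**2. Size of the effect.** The protocol gives no between-centre variance and no prognostic strength for any covariate, so these are assumptions:

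- latent-scale ICC for centre 0.01, 0.03 or 0.10. The between-centre SD on the log-odds scale is √(ICC/(1 - ICC) × π²/3), so 0.18 at the low end and 0.60 at the high end;
- severity score odds ratio 1.3, 1.7 or 2.2 per SD;
- age odds ratio 1.5 and hypoxaemia odds ratio 1.3 per SD, both already in the planned model;
- covariates uncorrelated.

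Trials of 1656 patients in 60 unequal centres were simulated with permuted blocks of 4 or 6 within centre and 40% against 32% mortality, 220 trials per setting. The table gives the ratio of mean Z to that of the planned model on the same data.

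| ICC | Centre only | Score only (OR 1.3 / 1.7 / 2.2) | Both (OR 1.3 / 1.7 / 2.2) |
|---|---|---|---|
| 0.01 | 1.000 | 1.007 / 1.028 / 1.058 | 1.008 / 1.028 / 1.058 |
| 0.03 | 1.003 | 1.007 / 1.028 / 1.057 | 1.011 / 1.031 / 1.060 |
| 0.10 | 1.020-1.022 | 1.007 / 1.025 / 1.052 | 1.029 / 1.046 / 1.073 |

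**3. Convert to power.** Taking the planned model to sit at the design's 90.0%, multiply the expected Z of 3.39 by each ratio g, apply the stated boundaries, and take the equivalent sample size as 1656 / g².

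| Model | g | Power | Equivalent N |
|---|---|---|---|
| Planned | 1 | 90.0% | 1656 |
| Add centre | 1.000-1.022 | 90.0-91.2% | 1656-1585 |
| Add score | 1.007-1.058 | 90.4-92.9% | 1633-1479 |
| Add both | 1.008-1.073 | 90.4-93.5% | 1630-1438 |

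This conversion treats Z as having unit variance. At ICC 0.10 the ratio of mean Z to its own SD rose by only 0.1-0.4% when centre was added, so most of that 2% is a correction of the standard error. The 91.2% is therefore an upper figure.

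**4. Type I error.** In 1000 null simulations at ICC 0.10 the planned model gave an SD of Z of about 0.96 and about 4.5% rejection at ±1.96. At ICC 0.01-0.05 the effect was within simulation noise. With 1708 / 60 = 28.5 patients per centre, fixed centre effects add 59 parameters for 60 centres; under the null they gave an SD of Z of 1.00-1.05 and about 5-6.5% rejection. The random intercept did not inflate the error: in a separate run of 500 at ICC 0.10 it rejected 5.0%, against 4.4% for the planned model.

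**The case against.** The strongest reply has four parts.

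- **Centre may be left to the analysis plan.** The sentence in section 10.2 lists prognostic covariates. Centre is a design factor, and the wording does not expressly exclude it. This has some force: an analysis plan could add a centre term. But section 10.2 presents the primary model as a finished specification with two named covariates, and a reader implementing it would fit no centre term. The cheapest place to settle this is that sentence.
- **Two covariates are a legitimate choice.** True. Omitting SOFA or APACHE II contradicts nothing in the protocol and is not an error. The point is that a likely gain is passed over without explanation.
- **A multi-component score can be missing.** This also stands. Section 3.3 expects more than 95% completeness only for the primary outcome, and section 10.2 itself foresees missing baseline subgroup data. A score in the primary model therefore needs a rule for missing values, and adding it is not entirely free.
- **The gain from centre is trivial and that from the score is assumed.** Largely right. Centre adds nothing visible to Z at ICC 0.01, 0.3% at 0.03 and about 2% at 0.10. Most of the gain comes from the score, whose strength the protocol does not give.

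A reader might infer that the trial is underpowered, or that its 90% claim fails because of the omissions. The protocol does not support this: the calculation is unadjusted and reproduces. Nor is there a false-positive risk, since omitting centre makes the test conservative if it changes it at all.

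**Conclusion.** The point holds in a limited form. The primary model omits the only stratification factor and a severity score already collected, and gives no reason. The 1656 patients, the maximum of 1708 and the 90% power stand as stated.

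What is forgone is about 0 to 1.2 percentage points of power for centre alone and about 0.4 to 3.5 points for centre and a score together. These are ranges over assumed inputs with material simulation error (220 trials per setting), not estimates for this trial. Correlation of the score with age or hypoxaemia would reduce the gain.

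Confidence is high on the omission and on the direction of the effect, and moderate on its size. For centre, the better argument is that the analysis should reflect the randomisation and give a correctly sized standard error; the power gain is small. A too-large standard error describes the omission of centre only, not that of the score.

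**What to change.** Before the first interim analysis, change the sentence in section 10.2 to read: logistic regression with a random intercept for centre, adjusted for age, severity of hypoxaemia and one pre-specified continuous baseline severity score (for example SOFA). State that the same model is used at every look, and carry it into the analysis plan. Use a random intercept and not fixed centre effects, given about 28 patients per centre. If the sponsor prefers to keep the present model, it should state why centre and illness severity are left out.

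The cost is one sentence and no new data. The mixed model is slightly harder to fit, so a fallback for non-convergence should be named. Some scores may be missing, so a simple pre-specified baseline imputation, made without regard to arm or outcome, is needed to keep all randomised patients with a known outcome in the analysis. The odds ratio then becomes conditional on centre and the score. A standardised absolute risk difference, on the scale of the 8-point target, is an optional addition and not part of the defect.

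### The only age analysis of treatment effect that the protocol names splits age at 65 without a reason; if the effect changes steadily with age, a test on that split loses roughly 5 to 25 points of interaction power

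*Protocol*

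**What the plan says.** Protocol 10.2 lists the subgroup analyses of 60-day mortality. For age it fixes the grouping: "Subgroup analyses will be provided on the primary outcome, for baseline patients features age category (≤65 years vs. >65 years"). Several other features in the list, such as illness severity, severity of hypoxaemia and number of comorbidities, are named without cut-points. The section gives no rationale for 65, names no interaction test, and mentions no analysis of treatment effect over continuous age.

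The same section says that the primary logistic model is "adjusted for age, and severity of hypoxaemia at baseline as two pre-defined baseline prognostic covariates". It does not say whether age enters as a continuous or a grouped variable.

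Exact age will be available. Section 7.2 says "Baseline data will be recorded (Age, sex, height" and further items, and section 8.1 lists "date of birth; sex at birth" among the baseline data.

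The sample size is set for the main effect: section 10.1.3 aims "to achieve a power of 90%, for the primary outcome of mortality at 60 days". No power is given for any subgroup or interaction analysis, and no age distribution is given.

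**The concern.** Whether the effect of dexamethasone on mortality differs with age is a question the trial has chosen to pre-specify. Answering it with one split treats a 64-year-old and a 66-year-old as different, and a 20-year-old and a 64-year-old as the same. If the effect changes gradually with age, the split discards information that has already been collected, and the answer depends on where the line falls.

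Interactions have much less power than main effects in a trial sized for the main effect, so an avoidable loss matters more here than elsewhere. A real age gradient could be missed. The stake is limited to this supportive analysis.

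**Working it through.** **1. The plan's own figure.** Section 10.1.1 says "we expect 40% control arm mortality at 60 days", and section 10.1.2 takes an absolute reduction of 8 points, hence 40% v 32%. With 90% power, two-sided 5% and the pooled-variance formula, n per arm = [1.96·√(2·0.36·0.64) + 1.2816·√(0.40·0.60 + 0.32·0.68)]² / 0.08² = 755 after rounding up, so 1510 in a fixed design. Hwang-Shih-DeCani parameters of −4 (efficacy) and −2 (futility, non-binding) are not stated in the protocol, but they return its stated bounds. They give an inflation of 1.0964, and 1510 × 1.0964 ≈ 1656. Then 1656/0.97 = 1707.2, so 1708 over two equal arms. The stated 1656 and 1708 reproduce, and N = 1656 is used below.

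**2. Information kept by the split.** For a normally distributed age and an interaction linear in age, cutting at 65 multiplies the interaction z-statistic by r = φ(c)/√[p(1−p)], where c = (65 − mean)/SD and p is the proportion above 65. The information kept is r².

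- Mean 60, SD 15: c = 0.333, p = 0.37, r = 0.782, r² = 0.61.
- Mean 55, SD 15: r = 0.735, r² = 0.54.
- Mean 65, any SD: r = 0.798, r² = 0.64.

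Large-sample logistic calculations at N = 1656 give about 0.58 to 0.66. Together this is about 55 to 65%.

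**3. From information to power.** Power with the split = Φ[r(1.96 + z_power) − 1.96], where z_power is the normal quantile of the continuous-age power. For mean 60, SD 15:

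- Continuous power 50%: Φ(0.782 × 1.96 − 1.96) = Φ(−0.43) = 33.5%, a loss of 16.5 points.
- Continuous power 80%: Φ(0.782 × 2.80 − 1.96) = Φ(0.23) = 59.1%, a loss of 20.9 points.

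For means of 55 to 65 and SDs of 15 to 18, the loss is about 6 to 7 points when continuous-age power is 20%, 15 to 20 at 50%, and 19 to 26 at 80%.

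**4. Simulation.** Logistic regression, N = 1656, 40% v 32% at the mean age, prognostic slope 0.3 log-odds per decade, 1500 trials per row, two-sided 5%. The test of treatment by continuous age is compared with that of treatment by age over 65. With 1500 trials each power has a standard error of at most √(0.25/1500) = 1.3 points.

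| Assumed age | Interaction odds ratio per decade | Continuous | Split | Loss |
|---|---|---|---|---|
| 60 (SD 15) | 1.13 | 35.7% | 24.3% | 11.4 |
| 60 (SD 15) | 1.16 | 53.4% | 36.7% | 16.7 |
| 60 (SD 15) | 1.22 | 74.9% | 54.6% | 20.3 |
| 60 (SD 15) | 1.28 | 91.0% | 72.5% | 18.5 |
| 62 (SD 14) | 1.08 | 17.5% | 12.6% | 4.9 |
| 62 (SD 14) | 1.22 | 67.8% | 49.4% | 18.4 |
| 55 (SD 16) | 1.08 | 21.5% | 14.9% | 6.6 |
| 55 (SD 16) | 1.22 | 80.1% | 55.0% | 25.1 |

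Odds ratios of 1.13, 1.16, 1.22 and 1.28 are about 0.12, 0.15, 0.20 and 0.25 on the log scale. With no interaction, the rejection rates were 4.9% (continuous) and 4.5% (split), so neither test gains by a looser error rate.

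**5. Large-sample check without simulation noise.** 40% v 32% overall, prognostic slope 0.35 per decade, interactions of 0.10/0.15/0.20/0.25 per decade.

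- Age 60 (SD 15): 24/46/69/86% continuous, 17/32/50/68% split.
- Age 55 (SD 16): 27/50/73/89% continuous, 17/33/51/69% split.
- Age 65 (SD 15): 23/45/67/84% continuous, 17/32/49/67% split.

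The losses, by subtraction, run from 6 to 22 points.

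**6. The opposite case.** If the true modification is a step exactly at 65, of 0.3, 0.5 or 0.7 log-odds, continuous age has power of 20.7%, 47.1% and 73.8%, against 29.6%, 64.9% and 89.2% for the split. The continuous test then loses 8.9, 17.8 and 15.4 points.

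**The case against.** The protocol does not fix the test being criticised. It says that subgroup analyses will be provided and names no model, interaction test or decision rule. A reader might infer that effect modification by age is examined only through the split. The text does not say so: estimates in two age bands are compatible with a continuous interaction term in the statistical analysis plan, which section 10.2 promises before the first interim analysis. A reader might also infer that age is already continuous in the primary model, so that the split is inconsistent with it. The form of that covariate is not stated. Both points stand. What remains is that the protocol does state one handling of age, and that it is the less efficient one for a graded effect.

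The larger losses also need strong interactions. The design effect is ln(0.32/0.68) − ln(0.40/0.60) = −0.35 log-odds. An interaction of 0.20 per decade would take that from its average to nil in 0.35/0.20 ≈ 1.7 decades and reverse it beyond. At 0.10 per decade, power is 22 to 27% against 16 to 17%, so neither version answers the question well. This stands and limits the practical gain.

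Finally, preferring continuous age rests on a gradual effect, which the documents neither support nor refute. Under a step at 65 the loss is of similar size in the other direction, and a row of estimates shown without a test would not recover it. This also stands, and the fix has to allow for it.

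**Conclusion.** The point holds as a minor, conditional one. The protocol names a single age analysis of treatment effect, split at 65 with no stated reason, although exact age is collected. If the effect changes steadily with age, a test on that split keeps about 55 to 65% of the information and loses roughly 5 to 25 points of power.

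That range assumes a mean age of 55 to 65, an SD of 14 to 18 and interactions of about 0.10 to 0.25 log-odds per decade. None of these is in the documents, so the figure cannot be read as a known loss in this trial. A younger, narrower population (mean 55, SD 12) could lose up to about 30 points.

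It would go too far to say that the protocol rules out a continuous analysis, or that the trial's conclusions are at risk. The primary analysis, its power and its type I error are untouched. This is a cheap improvement rather than a correction of an error.

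**What to change.** In section 10.2, and in the statistical analysis plan before the first interim analysis, add a pre-specified interaction between treatment and continuous age in the primary logistic model. Make it linear, with a spline in age as sensitivity check, name it as the main assessment of effect modification by age, and show the estimated treatment effect across the age range. Enter age in that model as a continuous covariate.

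Keep the two-group estimates, with their interaction p-value, as a secondary row of the forest plot. This supports the case of a step near 65, where the continuous test would lose about 8 to 18 points. Stating in advance which of the two is the main assessment avoids choosing between them after the results are seen. If there is a reason for 65, give it in one sentence.

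The cost is a few lines of text and one model term. No new data, no extra participants and no change to trial conduct are needed.
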